C2. Study design. Participants will be randomly assigned to SBT or ABBT. Treatment will be delivered in 75-minute, small (12-15 participants), closed-group sessions. Groups will be held weekly in months 1-3, biweekly in months 4-6, and monthly in months 7-12, for a total of 25 sessions. Assessments will occur at months 0 (baseline), 1 (midpoint 1), 3 (midpoint 2), 6 (midpoint 3), 12 (post-treatment), and 24 (1-year follow-up).

C3. Alternative designs considered. While we considered a shorter treatment duration (to reduce burden and increase disseminability), we ultimately chose a 25-session treatment for three reasons. First, 25 sessions over 1 year is about the modal length and the recommended intensity for gold standard weight loss treatment. Second, this length is consistent with the increasingly-supported chronic care model of obesity.¹⁵⁷ Third, clinical trial experts have recommended that, for initial tests of efficacy, treatments should be evaluated at full potency to reduce the likelihood that failure occurs because of sub-optimal dosage.¹⁵⁸ If ABBT improves weight loss outcomes for BED, methods for reducing the intensity (e.g. optimization and refinement of session content) and increasing the scalability (e.g. use of alternative delivery methods and/or non-experts clinicians, both of which have been successfully completed with ABBTs for other disorders¹⁵⁹) can be explored in future studies. We also considered including a second follow-up assessment, but determined that given the time needed to recruit and treat 130 participants with BED, a longer follow-up period would not be feasible.

Timeline	Year 1			Year 2			Year 3			Year 4			Year 5			R = recruitment
Manual refinement	X	X														
Therapist training	X															A = assessment (A ₁ , A ₂ , A ₃ , A ₄ , A ₅ = months 0, 3, 6, 12, 24, respectively).
Wave 1	R	A ₁	A ₂	A ₃		A ₄			A ₅							
Wave 2		R	A ₁	A ₂	A ₃		A ₄			A ₅						
Wave 3			R	A ₁	A ₂	A ₃		A ₄			A ₅					
Wave 4				R	A ₁	A ₂	A ₃		A ₄			A ₅				
Wave 5					R	A ₁	A ₂	A ₃		A ₄			A ₅			
Wave 6						R	A ₁	A ₂	A ₃		A ₄			A ₅		
Data analysis														X	X	
Manuscript preparation														X	X	
Planning future studies, e.g. optimization														X	X	

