Participants will be screened by phone to assess preliminary eligibility. Phone screens will use questions from the Mini International Neuropsychiatric Interview (MINI)¹⁶³ to assess psychiatric comorbidity and will be conducted by trained graduate students, similar to procedures used successfully in our other NIH-funded trials. Those who appear eligible will attend an orientation session where they will receive detailed information about the study. At a subsequent clinic visit, eligibility will be verified, informed consent obtained, and the baseline assessment completed. The enrollment process will provide participants with an adequate opportunity

to determine whether the assessment burden and demands of the program are acceptable; this is expected to reduce attrition. After the baseline assessment, participants will be randomized to condition in blocks of 6, stratifying by BMI category (<30, 30-40, and >40), sex, race/ethnicity, and frequency of binge episodes.

C6. Therapy conditions. We decided to use SBT as our control condition given that weight loss is our primary outcome. We considered including CBT as an alternative control condition, but ultimately decided that CBT would be a sub-par control because this treatment does not directly encourage weight loss and consistently produces minimal to no weight loss for patients with BED.

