Primary Aim (Efficacy of ABBT). Analyses will be conducted via linear mixed effects models for longitudinal data, which increase power by fully exploiting the strong correlation in treatment outcomes of interests (i.e., primarily, percent weight loss and secondarily, percent binge frequency reduction) across time. Patterned covariance matrices as implemented in SAS/STAT PROC MIXED V9.2 will be used to evaluate between group differences for percent weight loss and percent binge reduction across the study as a whole, and at each assessment post-baseline.²²⁵ Separate variance components will be used to capture therapist and participant-within-therapist variation. The within-subject covariance matrix will be assumed common across study arms, with an exponential variance function to deal with heteroscedasticity and a continuous-time AR(1) correlation matrix to accommodate residual autocorrelation over the unequal-size time intervals between follow-ups. Outcomes at all six time points will be estimated jointly for maximum statistical efficiency in the presence of intermittent missingness and loss to follow-up. The model will include random effects for subject and time (with higher-order effects if needed to capture nonlinear change), and fixed effects for treatment arm, time by treatment interaction, demographic information, and baseline values of weight, dietary intake and physical activity. Time-specific covariate-adjusted contrasts will be used to compare outcome between groups.

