Missing data. Our likelihood-based estimation methods remain unbiased when missingness is related to previously-observed outcomes as well as model covariates.²³⁶ If loss to follow-up is related to the missing outcome itself (an assumption that by its very nature cannot be tested empirically), we will use sensitivity analyses based on multiple imputation models²³⁷ to explore how robust our findings are with respect to a range of assumptions regarding missing data. We feel that these approaches are superior to alternatives (such as including only subjects with complete data or assigning a pre-specified score to the missing data) because these methods typically generate tests that are less powerful than the tests used assuming random censoring. We have experience with each of these approaches for handling non-ignorable non-response, and will analyze the data using several of these methods, which incorporate varying assumptions about the missing observations. To determine the extent to which the pattern of missing data might influence our findings, two approaches will be used. Compliance rates will be calculated for each participant. Participants with markedly low compliance rates (e.g., attendance at fewer than 3 assessments) will be considered for exclusion from analyses. Secondly, pattern mixture models^{169, 172, 174, 175} based on a random regression model (RRM)^{238, 239} will be used to examine the impact of missing data patterns on all variables. Subjects will be divided into groups based on their missing data pattern following the guidelines provided by Hedeker & Gibbons.²⁴⁰ The influence of missing data patterns on key variables will then be evaluated using RRM by comparing groups. If missing data patterns are found to be associated with key variables, this variable will be used as a covariate in subsequent analyses.

C11. Power Analyses

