Improving Weight Loss Outcomes for Binge Eating Disorder
Statistical Analysis Plan
NCT03712462
March 18, 2024

Statistical Analysis Plan

Statistical analyses were completed using R software version 4.1.3. Data were imputed via two methods to address missingness. Single imputation was used to impute weight measurements using a return-to-baseline approach, with dropouts assumed to have regained 0.15lb per week up to their baseline weight, consistent with assumptions used by other weight loss clinical trials (Wing et al., 2006). Other missing variables were imputed using R “mice” package (Van Buuren & Groothuis-Oudshoorn, 2011). Descriptive statistics were generated for all variables at each assessment point by treatment condition. There were no differences in age, sex, racial or ethnic status, and therapist credentials between treatment conditions.

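### The protocol lets randomised participants be excluded for low assessment attendance, and neither document says that everyone randomised is analysed

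*Protocol*

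**What the plan says.** The missing-data part of Protocol C10 says: "Participants with markedly low compliance rates (e.g., attendance at fewer than 3 assessments) will be considered for exclusion from analyses". The sentence is the first of two steps introduced by "To determine the extent to which the pattern of missing data might influence our findings, two approaches will be used"; the second is pattern-mixture modelling. It does not name the analyses concerned or fix the threshold. It does not say who decides, whether that person knows the arm, or whether baseline counts as an assessment.

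Protocol C2 schedules six assessments, at months 0, 1, 3, 6, 12 and 24. Protocol C5 places randomisation after the first: "After the baseline assessment, participants will be randomized to condition in blocks of 6".

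The rest of C10 is built to keep partial data. For the primary model: "Outcomes at all six time points will be estimated jointly for maximum statistical efficiency in the presence of intermittent missingness and loss to follow-up". For missing data: "Our likelihood-based estimation methods remain unbiased when missingness is related to previously-observed outcomes as well as model covariates".

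The SAP, dated 2024 and written in the past tense, imputes weight with "dropouts assumed to have regained 0.15lb per week up to their baseline weight" and imputes other variables with the mice package. It mentions no attendance-based exclusion. Neither document defines an analysis set or makes an intention-to-treat statement, and the SAP does not give the numbers randomised and analysed.

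**The concern.** Five of the six assessments come after randomisation, so the number attended can be affected by the assigned treatment. Selecting the sample on it means that the groups compared may no longer be the groups randomised. If baseline counts, fewer than three assessments means baseline plus at most one later visit, so the option falls on early dropouts.

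The protocol gives some reason to think that attendance could depend on arm and on progress:

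- In the team's earlier ABBT versus SBT trial (C1, Mind Your Health I), session attendance averaged 81.7% with ABBT and 73.9% with SBT. These are sessions, not assessments, but C9 aims to place midpoint assessments next to sessions.
- A5 suggests, tentatively, that disappointment with weight loss may partly explain dropout from behavioural weight loss programmes.

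At stake is the primary comparison of percent weight loss. Because the option is discretionary and has only an example threshold, a reader also cannot tell from the plan who would be in the analysis.

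**Working it through.** **The plan's own figures.** Protocol C11 requires 104 participants and allows 20% attrition: 104/(1 − 0.20) = 130, which reproduces. The target is 3.5 percentage points at d = 0.46, so the implied SD is 3.5/0.46 = 7.6 points. No exclusion rate or outcome gap is given, so everything below except the SD and the 65 per arm (130/2) is assumed.

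**General expression.** Let e be the share excluded in an arm and g the mean weight loss of kept minus excluded participants, taken as equal in the two arms. The full-arm mean is the kept mean minus e × g. Excluding therefore shifts the arm difference by

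bias = g × (e_ABBT − e_SBT).

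- Equal exclusion with the same gap: g × 0 = 0.
- g = 3 and a 5-point difference in exclusion: 3 × 0.05 = 0.15 points, 4% of 3.5.
- g = 7.6 and a 20-point difference: 7.6 × 0.20 = 1.5 points, 43% of 3.5.

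**Assumed worst case.** One arm loses its worst early responders, the other loses people at random, and there is no true difference. With early-to-month-12 correlation ρ and excluded share p, the kept mean in the selective arm rises by ρ × SD × φ(z_p)/(1 − p).

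- p = 0.10: 7.6 × φ(z)/(0.90) = 1.48. Times ρ = 0.3 to 0.7, this is 0.44 to 1.04 points.
- p = 0.20: 7.6 × φ(z)/(0.80) = 2.66. Times ρ = 0.3 to 0.7, this is 0.80 to 1.86 points.
- Against the target: 0.44/3.5 = 13% and 1.86/3.5 = 53%.
- p = 0.05, for comparison: about 0.25 to 0.6 points, or 7-17%.

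**Simulation with no true difference** (65 per arm, SD 7.6, two-sample t-test at 0.05, 5,000 runs). Poor responders are the more likely to be excluded, with the stated correlation.

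| Correlation with outcome | Excluded, ABBT / SBT | Bias (points, absolute) | Rejection after exclusion | Rejection, everyone kept |
|---|---|---|---|---|
| 0 | 5% / 15% | about 0 | 4.6% | 4.5% |
| 0.5 | 10% / 10% | about 0 | 4.5% | 4.9% |
| 0.5 | 5% / 15% | 0.6 | 7.1% | 5.2% |
| 0.8 | 5% / 15% | 1.0 | 12.9% | 4.7% |
| 0.5 | 2% / 20% | 1.15 | 13.0% | 5.3% |

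The arm that loses more of its poor responders looks better. Bias needs both conditions: unequal exclusion (or an unequal gap) and a link to outcome.

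**Balance alone is not a guarantee.** If excluded participants in both arms would have been scored at baseline (an assumption), then with a real difference the gap is larger in the better arm. Dropping a share e from each arm then multiplies the difference by 1/(1 − e): 1/0.90 = 1.11 at 10% and 1/0.80 = 1.25 at 20%.

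**The case against.** The strongest reply is that the later document has overtaken the sentence. The protocol said only that exclusion would be considered, with an example threshold, within a pair of steps for judging the influence of missing data. The SAP then lists two methods for missingness, both imputation. Imputing dropouts' weights implies that dropouts stay in the weight analysis. Much of this stands, and it is why the point concerns an open option and an unstated analysis set, not an exclusion known to have happened.

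Several stronger readings are tempting, and the documents do not support them:

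- *Participants were excluded and the result is biased.* Nothing says so, and the SAP points the other way for weight.
- *The choice rests with analysts who have seen the data by arm.* The documents do not say who decides or whether they are blinded.
- *The exclusion undermines the missing-at-random basis of the primary result.* That applies to the 2017 likelihood plan. The SAP's weight analysis uses an assumed regain instead.
- *C10 contradicts itself.* It says "We feel that these approaches are superior to alternatives (such as including only subjects with complete data", and gives reduced power as the reason. Dropping people with fewer than three of six visits is not a complete-data analysis. The two sit uneasily together but do not contradict.

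The worst-case figures are also open to challenge. The documents do not suggest selective dropout in one arm and random dropout in the other. Excluding 20% would use up the protocol's whole attrition allowance, and C1 reports 82.6% retention at 12 months in Mind Your Health II. The calculations take complete month-12 data as the benchmark. Early dropouts lack those data under any method, so keeping them would not remove all of the calculated bias.

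One thing is not answered: the SAP does not withdraw the option, and no text says that all randomised participants are analysed.

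**Conclusion.** The point holds as a gap that should be closed. The protocol permits a discretionary exclusion on a post-randomisation variable and does not confine it to a sensitivity analysis. Used in the main comparison, it can bias the result if exclusion differs by arm and relates to outcome. The SAP makes its use for weight unlikely but does not rule it out.

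The size cannot be derived from the documents. It is about zero when exclusion is balanced with the same outcome gap, or is unrelated to outcome. It reaches about 0.4-1.9 points (13-53% of the 3.5-point target) only under the assumed worst case of 10-20% exclusion, selective in one arm and random in the other. A reader might take that range as the expected bias. It is an upper scenario built on assumed exclusion rates, correlations and mechanism, and should be cited only as such.

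**What to change.** 1. State that the primary analysis includes all randomised participants in their assigned arm, under the planned missing-data method.
2. Delete the attendance exclusion, or confine it to a labelled sensitivity analysis with a fixed threshold and a statement of whether baseline counts. Low attendance can still be described.
3. Because the SAP describes completed analyses, report the numbers randomised, excluded and analysed by arm for each outcome. If anyone was excluded on attendance, rerun the analysis with them included.

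The wording change is a sentence or two. It needs no new data and leaves the target of 130 unchanged. A rerun is needed only if the counts show exclusions.

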Primary Aim (Efficacy of ABBT). The study's data will consist of repeated assessments over time within randomized individuals within each treatment condition. Therefore, power calculations are dependent on both an expected difference between treatment arms as well as the clustering of the data (repeated observations within an individual with up to six repeated measures per participant within one of the two treatment conditions), resulting in a multilevel model structure. Using the method described by Raudenbush²⁵²⁻²⁵⁴ and implemented with the software Optimal Design, power calculations were made for this multilevel model structure. No results are available which directly compare the effect of ABBT and SBT on weight loss in BED patients. However, effect size can be predicted by deriving effect sizes from trials with elements similar to the proposed study, e.g., percent weight loss comparison between ABBT and SBT from the Mind Your Health II study (effect size at 12 months $d=0.39$) and percent weight loss and binge reduction comparison of CBT vs. SBT ($d=0.625$; 30% difference in binge reduction rates).⁶⁴ Based on previous studies, we aim to detect a clinically meaningful difference for both weight and binge eating frequency (3.5% weight loss between groups ($d=0.46$) and a difference in 4 binge eating episodes over the 4-week time period). Baseline covariates that can account for variability in the trial outcomes were taken into consideration in the power analysis. Given these assumptions, a sample size of 104 (52 for each group) is required for 80% power with the significant level of 0.05 and five assessment points, assuming the ratio of the variability of level-1 coefficient to the variability of level-1 residual is one. While allowing for up to 20% attrition, the proposed sample size of 130 is adequately powered to examine a clinically meaningful difference between treatment conditions for both percent weight loss and frequency of binge episodes. We believe this power estimate to be conservative given: 1) attrition estimates are greater than the team has achieved in similar weight control studies; and 2) missing values will be imputed using multiple imputation to maximize the number of the observations used to estimate models.

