Mixed effects models were conducted for Primary Aim 1 (Efficacy of ABT) and Secondary Aim 2 (Between-Subjects Moderation) given nested data within subjects and group. The R “merTools” package was used for models predicting percent weight change and global eating disorder psychopathology change (Knowles et al., 2023), and the R “cplm” package was used for models predicting binge eating frequency change (due to zero-inflated distribution of percent binge eating change at post-treatment and follow-up) (Zhang, 2013). Models for percent weight and binge eating change included fixed effects for the interaction between linear or quadratic time effects and treatment condition (and baseline moderators for Secondary Aim 2). Only linear time effects were included in the models for global eating disorder psychopathology, since the quadratic time fixed effect did not significantly improve model fit. Model selection criteria (e.g., Aikaike information criteria, Bayesian information criteria) and significance testing were used to identify the random effects structure that best fit the model. For percent weight change, models included separate random effects for intercept and slopes of quadratic time effects nested within subjects. For binge eating frequency change, models included random effects for intercept nested within subjects. For global eating disorder psychopathology change, models included separate random effects for intercept and slopes of linear time effects nested within subjects. No differences in results were observed when treatment format delivery (i.e., telehealth vs. in-person groups) was included as a covariate; therefore, results without the inclusion of treatment format delivery as a covariate are reported. Statistically significant interactions were interpreted by plotting simple regression lines for each variable. For all linear mixed effects models, alpha was set at 0.05 and confidence intervals were obtained. Cohen’s f^2 effect size measures were estimated for group x time interaction using methods described by Selya and colleagues (Selya et al., 2012), with $f^2 \geq 0.02$, $f^2 \geq 0.15$, and $f^2 \geq 0.35$ representing small, medium, and large effect sizes, respectively.

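### The 80% power in Protocol C11 makes no allowance for between-group variance, although treatment is delivered in closed groups nested within arm

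*Protocol*

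**What the plan says.** Protocol C11 (Primary Aim) describes the data as visits within randomized individuals within arms. The only clustering it names is "the clustering of the data (repeated observations within an individual with up to six repeated measures per participant". From a target of 3.5 percentage points (d = 0.46) it concludes that "a sample size of 104 (52 for each group) is required for 80% power with the significant level of 0.05 and five assessment points". It then allows for up to 20% attrition and sets N at 130. It calls the estimate conservative for two reasons: assumed attrition is above what the team has seen, and missing values will be imputed. It gives no group count, group size or group ICC.

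The delivery unit is in C2: "Treatment will be delivered in 75-minute, small (12-15 participants), closed-group sessions". There are 25 sessions over 12 months, and C5 sets six recruitment waves. The two conditions follow different manuals (C6), so a closed group belongs to one arm.

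The analysis sections do place structure above the participant. C10 says "Separate variance components will be used to capture therapist and participant-within-therapist variation", and C8 balances clinicians across conditions. The SAP justifies mixed models as "given nested data within subjects and group", but the random effects it then lists for each outcome are within subjects only.

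**The concern.** Members of a closed group share leaders, peers, calendar period and a year of sessions, so their outcomes may be correlated. A therapist effect common to both arms largely cancels when clinicians are balanced across conditions. A group effect does not cancel, because each group contributes to one arm only, and it adds directly to the variance of the arm difference. A calculation that treats 104 completers as independent omits that variance.

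Two things are at stake. If the analysis accounts for groups, its power is below the printed figure, and a null result would seem to rule out a 3.5-point difference more firmly than the design allows. If the analysis ignores groups, the nominal 5% error rate is not held.

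**Working it through.** **Inputs.** From C11: alpha 0.05 (two-sided assumed, since sidedness is not stated), 80% power, 104 completers, d = 0.46, variance ratio one, 20% attrition, N = 130. From C2: groups of 12-15. From C5: six waves. From C1 (Mind Your Health II): 82.6% retention at 12 months. The group ICC is not in the documents, so 0.01 to 0.10 is an assumed range.

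**Step 1: the plan's own figure.** The attrition step reproduces: 104/(1 - 0.20) = 130. The 104 does not:
- Two-sample comparison: 2 x (1.960 + 0.842)^2 / 0.46^2 = 74.2, so 75 per arm or 150 in all (152 with the t distribution). Power at 52 per arm is about 64-65%.
- Slope formula with five equally spaced visits and ratio one: variance factor 1 + 1/10 = 1.1, giving 166 in all, or 60% power at 104.
- Mean of 4-6 visits with an assumed within-person correlation of 0.5: 90-96 without baseline adjustment, 52-58 with it.

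C11 says covariates were taken into account but not how much variance they explain. Back-solving for 104 needs an R-squared of about 0.31 (t-test) or 0.375 (slope formula). The 104 is therefore unverifiable rather than shown to be wrong. From here the stated 80% is granted at ICC 0, which corresponds to a noncentrality of 2.828 on 102 df.

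**Step 2: number of groups (inferred).** C2's group size gives 130/15 = 8.7 to 130/12 = 10.8, about 9 to 11 groups. Six waves with one group per arm gives 12, of about 10.8 people each. Twelve groups of 12-15 would need 144-180 people, so these statements do not fit exactly. Nine, ten and twelve groups are all shown.

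**Step 3: power at 104 completers.** Design effect DE = 1 + (m - 1) x ICC, with m = 104/9 = 11.6, 104/10 = 10.4 or 104/12 = 8.67. The noncentrality becomes 2.828/sqrt(DE). Example with 12 groups and ICC 0.05: DE = 1 + 7.67 x 0.05 = 1.38, noncentrality 2.41, power 66%.

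| ICC | 9 groups | 10 groups | 12 groups | 12 groups, 10 df |
|---|---|---|---|---|
| 0 | 80% | 80% | 80% | 72% |
| 0.01 | 76% | 76% | 77% | 69% |
| 0.02 | 72% | 73% | 74% | 66% |
| 0.05 | 62% | 64% | 66% | 58% |
| 0.10 | 50% | 52% | 56% | 49% |

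The first three columns of power use individual-level df (102). On group-level df, power at ICC 0 is already 68% for 9 groups and 70% for 10.

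**Step 4: retention better than planned.** At 82.6% retention (0.826 x 130 = 107 completers), 80% holds only up to an ICC of about 0.003-0.004 on individual-level df, and power at ICC 0.02 is 73-75%. With all 130 retained, power at ICC 0.02 is 80-82% for 9 to 12 groups on individual-level df, but 67-74% on group-level df.

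**Step 5: if the test ignores groups.** Type I error is about 2 x [1 - Phi(1.960/sqrt(DE))]. For 10 to 12 groups this is about 6% at ICC 0.01, 7% at 0.02, 10-11% at 0.05 and 14-16% at 0.10. The rejection rate under the target effect falls much less than in Step 3. With 12 groups and ICC 0.05 it is about Phi((2.802 - 1.960)/sqrt(1.38)) = Phi(0.72), or 76%.

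**The case against.** Several objections stand and limit the point.

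- A reader might infer that the trial misses 80% unless group correlation is essentially zero. That is accurate only near 104 completers. C11 allows for up to 20% attrition, and with full retention an ICC of about 0.02 is absorbed on individual-level df. The slack is small at the retention that the team itself reports.
- A reader might take the percentages as the trial's true power. They are conditional on an 80% baseline that cannot be checked, on an assumed ICC and on an inferred group count. The SAP also mentions both telehealth and in-person groups, so the realised group structure is unknown.
- A reader might infer that the main danger is an over-read null result. Under the random effects that the SAP lists, the main consequence is false positives (Step 5).
- C11 does not name the software module, so a calculation without a group level is inferred from the levels and inputs it lists. The word group in the SAP is ambiguous, because the same paragraph uses it for treatment condition. The therapist component in C10 is not a group component.
- C11's two reasons for calling the estimate conservative make no claim about clustering.
- The SAP reports completed analyses, so a revised power figure cannot change the design.

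None of this brings group correlation into the power calculation. Neither attrition nor imputation addresses it, and the interpretation of the results can still be corrected.

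**Conclusion.** The point holds in this form: C11's 80% treats completers as independent although treatment is given in closed groups within arm, so it does not allow for between-group variance. At the planned 104 completers, any positive group ICC takes the power of a group-aware test below the granted 80%. The loss is about 6-8 points at ICC 0.02 and 14-18 points at 0.05 on individual-level df, and larger on group-level df. The direction is the same for 9, 10 and 12 groups. The size rests on the granted baseline and the assumed ICC.

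The documents do not show that 104 is wrong, that N should have been larger by a given amount, or that any one range is the trial's actual power.

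**What to change.** Leave N unchanged.

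- Recompute the C11 power with a therapy-group level, using the actual number and size of groups per arm, a stated ICC range, group-level df and the covariate R-squared that was used. Report the resulting range wherever the single 80% now stands. The figures above illustrate the size and are not the numbers to print.
- State that *conservative* refers to attrition and imputation only, not to group clustering.
- When reporting results, give the estimated group ICC and a group-adjusted confidence interval for the 12-month difference, read against the 3.5-point target.

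The cost is one recalculation, one group-adjusted estimate and a few sentences, with no new participants or data. The downside is a less favourable stated power.
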